Scheduling Window (Days)	-28 to -1	+/- 3	+/- 3	+/- 1	+/- 1	+/- 1	+/- 1	+/- 1	+/- 1	+/- 3	+/- 3	+/- 3	At time of Discontinuation	30 days Post discontinuation	3,6,9,12,18,24 months Post cyst
Study Treatment															
BCG*				X	X	X	X	X	X						
MK 3475		X	X	X			X			X	X				
Efficacy Measurements															
Cystoscopy ^o	X											X			X
Biopsy (if clinically indicated) ^o	X											X			X
Tumor Biopsies/ Archival Tissue Collection/ Correlative Studies Blood															
Specimen Collection ^p		X ^r	X	X	X	X	X	X	X	X	X	X			X ^p

^aScreening Visit: No study required procedures should be conducted (unless part of routine care) prior to the signing of the informed consent document. Screening Visit laboratory procedures may be used for Day 1 Cycle 1 if completed within 10 days of Day 1 Cycle 1. Restaging imaging of CT urogram or CT/ MRI of abdomen/ pelvis that occurs within 90 days of study entry is acceptable.

^bEarly Discontinuation Visit: All Subjects who discontinue treatment early for any reason should undergo all procedures listed in the Flow Chart for Discontinuation Visit.

^cIf a subject has completed all study treatment, the subject should complete the 30 day Safety Follow-Up Visit procedures listed in the Flow Chart.

^dFollow-Up Visits should occur at approximately 3, 6, 9, 12, 18, and 24 months from Week 19 cystoscopy. It is expected that follow up data will be collected from routine office visits which generally occur every three months in this population. There may be a shift in schedules if the participant has been given maintenance therapy or was found to have a recurrence. Subject will complete final set

Product: MK-3475

Protocol/Amendment No.: Amendment 5, 21 October 2019

of Questionnaires at the 3 month visit. Follow-Up information may be collected via medical record and document review only. However, patient contact via phone or in person may occur if information is not available via chart review.

^eSubject Identification card may be given at any time after consent process has occurred and prior to treatment on Day 1 Cycle 1.

^fPrior and concomitant medications will include any medications taken within the 28 days prior to consent and through the safety visit and will include prescribed, over-the counter and herbal/alternative remedies.

^gPost-study treatment anti-cancer therapy and recurrence status may be collected through follow-up chart review.

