8.1.6.2 Treatment Period

8.1.6.2.1 Dose Escalation

The first 3 enrolled patients will be treated with 100 mg of MK-3475 every 3 weeks for 6 cycles. If one subject of the three requires the dose of MK-3475 to be withheld or discontinued, the 100 mg cohort will be expanded to 6 subjects. If two out of three or two out of six subjects develop toxicity that requires the dose to be withheld or discontinued, the dose will not be escalated to 200 mg MK-3475 every 3 weeks. All remaining subjects will be treated at 100 mg MK-3475 every 3 weeks for 6 cycles.

Physical examination and assessment of toxicity will be performed before each administration of MK-3475. A CBC will be obtained on Day 1 of every 3-week cycle. Biochemistry panel examining electrolytes, and liver enzymes will be performed on Day 1, Cycle 1 of MK-3475, at Weeks 7, 10 and 13, and at the end of therapy (Week 19). Treatment will not proceed unless laboratory values are acceptable. Urinalysis will occur at weeks 7-12 prior to each BCG treatment. BCG treatment will not proceed unless urinalysis results are acceptable. Collect and record non-serious and serious adverse events and assignment of toxicity grade (NCI CTCAE, Version 4) at each visit. Collect and record any changes in concomitant medication.

Product: MK-3475

Protocol/Amendment No.: Amendment 5, 21 October 2019

Subjects will be provided with an oral thermometer and a diary (Appendix H) to document twice daily oral temperatures. The diary will also ask for documentation of other symptoms to help monitor for systemic infection of BCG.

The AUA IPSS and QOL questionnaires are to be administered at Day 1 Cycle 1 and Week 10 visit prior to any study procedures.

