8.1.6.4 Post-Treatment Visits

An evaluation under anesthesia with cystoscopy, cytology, and random bladder biopsies (if indicated for positive findings on cystoscopy or cytology) will be performed at Week 19 (approximately 6 weeks after the last dose of BCG) to assess for response. Physical examination, performance status, as well as vital signs, will also be assessed at the Week 19 visit. Laboratory assessments will include hematology and chemistry as outlined in Section 7 – Trial Flow Chart and Table 7. Coagulation assessment (PT/PTT/INR) will be re-assessed, if resection/biopsy is indicated. Specimens needed for correlative studies will again be collected, including blood, urine, saliva and tumor (if biopsy is performed). The collection, storage, and processing of laboratory samples are detailed in the Procedure Manual.

The AUA IPSS and QOL questionnaires are also to be administered at Week 19 visit prior to any study procedures.

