8.1.6.6 Follow-up Visits

Subjects who complete all study treatment or discontinue trial treatment for a reason other than disease progression will move into the Follow-Up Phase and should be assessed at 19 week cystoscopy. Additional follow up information will be collected at 3, 6, 9, 12, 18, and 24 months post completion of treatment. Every effort should be made to collect information regarding disease status, start of new anti-neoplastic therapy, disease recurrence, disease progression, death, or end of the study. Information regarding post-study anti-neoplastic treatment will be collected if new treatment is initiated.

A final set of AUA IPSS and QOL questionnaires are also to be administered at the 3 month Follow Up visit.

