For primary objective 1, the proportion of patients with each AE will be reported along with the NCI CTCAE Grade of the AE. The Quality of Life Questionnaire, which includes one question with seven categorical responses, will be described with frequencies and percentages. The American Urologic Association Symptoms Index Questionnaire, which includes seven questions each with a numerical score between 0 and 5 as well as a final numerical sum of all responses, will be described with measures of central tendency and dispersion. Due to the questionnaires being given at three time points (Pre-treatment, Mid-treatment, and Post-treatment), the responses may be analyzed to look for longitudinal effects over time for specific variables of interest with repeated measures ANOVA to evaluate changes and control for individual differences (*although this would be very low power due to n=15*).

For the secondary objective, subjects will be assessed at 19 weeks, 3 months, 12 months, and 24 months post treatment completion for complete response. The outcome endpoint will be complete response status at 19 weeks, 3 months, 12 months, and 24 months post treatment to measure complete response, recorded as yes or no and summarized as proportions and a percent.

Product: MK-3475

Protocol/Amendment No.: Amendment 5, 21 October 2019

These proportions/percent will be reported, but no statistical analysis will be performed as this is a single arm phase I study, and no control group is available for direct comparison.

For the exploratory objectives, Pearson or Spearman's rank correlation coefficient will be used to estimate correlations between expression level change and treatment outcome, as well as the correlations between mutation presence and treatment outcome.

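### The SAP's longitudinal questionnaire analysis assumes three time points, but the protocol schedules four and two of them fit the post-treatment slot

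*Combined protocol and SAP*

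**What the plan says.** Section 10.1 places both questionnaires under the primary objective. It commits to descriptive summaries: frequencies and percentages for the single quality-of-life item, central tendency and dispersion for the AUA scores. It then adds an optional longitudinal analysis, premised on "Due to the questionnaires being given at three time points (Pre-treatment, Mid-treatment, and Post-treatment" and carried out "with repeated measures ANOVA to evaluate changes and control for individual differences". The same sentence warns of very low power with 15 subjects. No SAS procedure, covariance structure or missing-form rule is given.

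The schedule is set elsewhere:

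- Section 8.1.6.2.1: "The AUA IPSS and QOL questionnaires are to be administered at Day 1 Cycle 1 and Week 10 visit prior to any study procedures".
- Section 8.1.6.4: "The AUA IPSS and QOL questionnaires are also to be administered at Week 19 visit prior to any study procedures".
- Section 8.1.6.6: "A final set of AUA IPSS and QOL questionnaires are also to be administered at the 3 month Follow Up visit".
- Section 7.1: the questionnaire row is marked at Weeks 1, 10 and 19 and in the follow-up column. Footnote d limits follow-up to one final set "of Questionnaires at the 3 month visit". Nothing is marked at the discontinuation or safety visits.

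**The concern.** An analysis over visits needs a defined set of visits. With four forms scheduled and three named, an analyst has to decide what to do with the extra one: use Week 19, use month 3, pool them, or model all four. In an open-label trial, that decision would be made with the data in view.

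The choice has some content. Section 5.2.1.4 says that irritative bladder effects usually appear after the third BCG instillation and tend to worsen with each further one. Week 10 is the fourth instillation visit and its form is completed before treatment, so that form reflects three instillations. Week 19 and month 3 are the only forms after the full course of six, and comparing them would show whether symptoms settle or persist.

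The second issue is missing forms. Classical repeated measures ANOVA in a one-row-per-subject layout keeps only subjects with every modelled form. With 15 subjects, a few gaps remove a visible share of the sample. If the gaps are related to toxicity, the subjects who remain may look better than the whole group.

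**Working it through.** **Step 1. Count the visits.**

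| Form | Source | Fits which SAP slot |
|---|---|---|
| Day 1, Cycle 1 | 7.1; 8.1.6.2.1 | Pre-treatment |
| Week 10 | 7.1; 8.1.6.2.1 | Mid-treatment |
| Week 19 | 7.1; 8.1.6.4 | Post-treatment (8.1.6.4 is the post-treatment visit section; last MK-3475 is at Week 16) |
| 3-month follow-up | 7.1 with footnote d; 8.1.6.6 | Post-treatment (the flow chart's post-treatment column) |

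The SAP's figure is 3 and the schedule gives 4, so the figure does not reproduce. The documents' own labels support either of the last two rows as the post-treatment form.

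**Step 2. Size the complete-case loss.** Inputs: 15 subjects (Sections 1.0 and 10.1). The documents give no completion rate, so assume that each form after baseline is completed with probability *p* of 85% to 95%, independently. Day 1 is taken as complete because it is filled in before any treatment.

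- Complete on four visits: 15 × *p*³
- Complete on three visits (Day 1, Week 10 and one later form): 15 × *p*²
- Forms available to a model that uses them all: 15 + 45*p*, out of 60

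| *p* | Four visits | Three visits | Forms of 60 |
|---|---|---|---|
| 0.85 | 15 × 0.614 = 9.21 | 15 × 0.7225 = 10.84 | 53.25 |
| 0.90 | 15 × 0.729 = 10.94 | 15 × 0.81 = 12.15 | 55.50 |
| 0.95 | 15 × 0.857 = 12.86 | 15 × 0.9025 = 13.54 | 57.75 |

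The three-visit column is the one that applies to the plan as written: a missed form at an unmodelled fourth visit drops nobody.

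**Step 3. What the loss means for precision (illustration only).** The SAP gives no alpha, power or SD for this analysis. For a paired change from baseline, assume a two-sided 0.05 test and take power as P(T > t₀.₉₇₅,ₙ₋₁), where T is noncentral t with *n* − 1 degrees of freedom and noncentrality *d*√*n*.

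| *n* | Change detectable with 80% power (SD of change) | Power for a 0.8 SD change |
|---|---|---|
| 15 | 0.78 | 82% |
| 13 | 0.85 | 75% |
| 11 | 0.94 | 67% |
| 9 | 1.07 | 56% |

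**Step 4. Are missed forms plausible?** Section 5.2.4 takes a subject off the trial if either drug is held for more than 2 weeks for toxicity. The flow chart marks no questionnaire at the discontinuation visit, and Section 8.1.6.5 lists none. Footnote d allows follow-up by record review alone, which does not in itself produce a patient-completed form. Missed forms are therefore foreseeable, and some could be related to toxicity.

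**The case against.** The strongest reply is that little depends on this analysis. It is optional, limited to variables of interest, and already described as very low powered. The committed analysis is descriptive, and Section 10.1 promises descriptive statistics for all study variables. A reader might infer that a collected form will be thrown away and the recovery information lost. The documents do not support that, because nothing excludes the 3-month form from the descriptive summaries. This part of the reply stands.

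A reader might also infer that the SAP commits to dropping incomplete subjects. It does not. Listwise deletion belongs to the classical multivariate layout, and the SAP neither specifies nor rules out an implementation that keeps partial data. The fair criticism is that the implementation and the missing-form rule are unspecified.

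The strongest tempting reading is that the analysis will make tolerability look better than it is. That is not demonstrated. Section 8.1.6.6 moves subjects who stop for reasons other than progression into follow-up, with assessment at Week 19 and month 3. Section 8.1.5.1 asks for the applicable final-visit activities at discontinuation, which could be read to include a form. Footnote d allows contact by phone or in person when the chart is not enough. Recurrence is a weak explanation for missing Week 19 forms, since those are completed before that visit's cystoscopy. Sections 5.2.4 and 7.1 still leave a risk, but its size and direction are unknown.

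Finally, three time points might be meant as three phases, with month 3 regarded as later follow-up. That is a possible intention, but the sentence is about when the questionnaires are given, and on that it disagrees with the schedule. None of these replies removes the count error.

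**Conclusion.** The visit count in Section 10.1 is wrong as written: the protocol schedules four administrations, and two of them qualify for the one post-treatment slot. This rests on the current text alone and needs no assumption.

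The point about method is conditional. If the ANOVA is run on complete cases, roughly 9 to 13 of 15 subjects would remain on four visits, or 11 to 14 on three. Both ranges assume a complete Day 1 form and independent 85% to 95% completion at each later visit. Missingness related to toxicity would not follow that independence assumption, so the figures show how quickly complete cases shrink and do not measure bias.

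The overall impact is minor to modest. The proportion of patients with each adverse event and its CTCAE grade, which is the main summary for the primary objective, does not depend on the questionnaires being complete.

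**What to change.** In Section 10.1, replace three time points with four and name them: Day 1 Cycle 1, Week 10, Week 19 and the 3-month follow-up. This also removes the ambiguity over which form is post-treatment.

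If the longitudinal analysis is done, replace repeated measures ANOVA for the AUA total with a linear mixed model: visit as a fixed effect, subject as a random effect, all available forms included. Report mean change from baseline with a 95% CI and the number of forms received at each visit. Keep the quality-of-life item as frequencies by visit.

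The mixed model avoids discarding partial data, but it does not correct for forms that are missing because of unobserved symptoms. The counts by visit let a reader judge that. If the sponsor prefers not to model 15 subjects, the named visits with descriptive change and counts would be enough.

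The cost is SAP wording and a different procedure in SAS 9.4. No new data or visits are needed.

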5.7 Subject Replacement Strategy

Subjects who have been screened and enrolled will be included in an intent-to-treat population. However, if a subject has been enrolled and subsequently treated or attempted treatment (IV insertion with MK-3475 preparation) with at least 1 cycle of MK-3475, the patient will not be replaced. If a screened subject withdraws prior to first treatment cycle, that subject may be replaced.

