8.1.4 Tumor Imaging and Assessment of Disease

Chest X-ray, computerized tomography (CT) urogram or magnetic resonance imaging (MRI) urogram are allowed to ascertain the superficial nature of the disease when indicated according to the standard of care. If urogram protocol not available or contrast allergy/poor renal function preclude such imaging, then non-contrast CT or MRI of the abdomen/pelvis within 90 days of study entry will suffice.

Disease assessment will occur via an evaluation under anesthesia with cystoscopy, cytology, and random bladder biopsies (if indicated for positive findings on cystoscopy or cytology). Assessment will be performed at week 19 (approximately 6 weeks after the last dose of BCG treatment). Assessment will also occur at 3 months, 6 months, 9 months, 12 months, 18 months, and 24 months post treatment visit as per standard of care for the local site. Due to recurrence or maintenance therapy, it is expected that assessments may not fit exactly at these time points. If assessment not completed at that time point, indicate not done on the case report form.

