8.1.6.5 Treatment Discontinuation/Safety Follow-Up Visit

The Treatment Discontinuation Visit and Safety Follow-Up Visit include identical procedures and assessments. Subjects withdrawn from treatment prior to completion of the Treatment Period should undergo a Discontinuation Visit for safety purposes and may occur any time within 30 days of the subject discontinuing treatment, but preferably prior to the subject initiating a new treatment. The mandatory Safety Follow-Up Visit should be conducted approximately 30 days after the last dose of trial treatment or before the initiation of a new anti-cancer treatment, whichever comes first. All AEs that occur prior to the Safety Follow-Up Visit should be recorded. Subjects with an AE of Grade >1 will be followed until the resolution of the AE to Grade 0-1 or until the beginning of a new anti-neoplastic therapy,

Product: MK-3475

Protocol/Amendment No.: Amendment 5, 21 October 2019

whichever occurs first. SAEs that occur within 30 days of the end of treatment or before initiation of a new anti-cancer treatment should also be followed and recorded.

Assessments at the Discontinuation/Safety Follow-Up Visit include a full physical examination, ECOG Performance Status and vital signs. Laboratory assessments include hematology, chemistry, and urinalysis, as well as evaluation of thyroid function. Concomitant medications and toxicity assessment will be recorded as well.

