10.0 STATISTICAL ANALYSIS PLAN

10.1 Statistical Analysis Plan Summary

A minimum of 15 subjects will be enrolled. Seventy percent of bladder tumors are superficial [22] indicating to enroll at least 15 patients, approximately 21-25 patients will need to be approached to meet eligibility and to allow for patient disinterest.

Fifty percent of those patients who respond to BCG treatment develop recurrent disease [30; 31] generally detected within 6 months of BCG treatment. Those patients with recurrent disease often are sent for radical cystectomy as there are no other acceptable standard treatment options. This study, though primarily evaluating maximum tolerated dose, will examine the percent response at 19 weeks to determine if MK-3475 has altered the pattern of responders as early as 19 weeks from the start of treatment. The results of this study will not only examine the safety of combining MK-3475 with BCG for future studies, but will also assist in determining patient eligibility (recurrent superficial bladder cancer versus initial diagnosis) and considerations for future study design.

Patient related data will be collected and transferred to an excel spreadsheet for statistical analysis. SAS software version 9.4 will be used for all data analysis. Descriptive statistics will be computed for all study variables. Continuous variables will be described with measures of central tendency (mean, median) and dispersion (range, standard deviation). Categorical variables will be summarized as frequencies and percentages. Some examples include tumor stage (Ta, T1, Cis), age, ECOG Performance Scale (0, 1, 2), sex, and use of tobacco and alcohol.

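### Section 10.1 limits complete response to bare percentages in about 15 subjects: no interval, no named denominator, and no rule for counting an assessment that was not done

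*Combined protocol and SAP*

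**What the plan says.** Section 3.2 makes the CR rate at 19 weeks and at the 3, 12 and 24 month post-treatment visits the single secondary objective. Section 10.1 says the 19-week response percentage will be examined "to determine if MK-3475 has altered the pattern of responders as early as 19 weeks from the start of treatment". Later in that section CR is a yes/no variable at each time point, summarised as a proportion and a percentage: "These proportions/percent will be reported, but no statistical analysis will be performed as this is a single arm phase I study". The sentence goes on to give the absence of a control group as the reason.

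On who is counted, Section 5.7 states: "Subjects who have been screened and enrolled will be included in an intent-to-treat population". It adds that a subject treated, or in whom treatment was attempted, "with at least 1 cycle of MK-3475, the patient will not be replaced". Section 10.1 does not refer to either group.

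On missing assessments, Section 8.1.4 expects some cystoscopies to fall away from the nominal times because of recurrence or maintenance therapy, and instructs: "If assessment not completed at that time point, indicate not done on the case report form". This is a recording instruction; no section turns it into an analysis rule. Section 8.1.6.6 says that subjects who complete treatment, and those who "discontinue trial treatment for a reason other than disease progression will move into the Follow-Up Phase and should be assessed at 19 week cystoscopy". It states no such route for subjects who stop because of progression.

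**The concern.** Two things are at stake. First, the stated aim asks more of the 19-week result than a percentage without an interval can give. A reader shown 53% from 15 subjects has no indication in the planned output of how loosely that figure is pinned down, although Section 10.1 intends the results to inform eligibility and the design of later studies.

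Second, the same data can yield different percentages depending on who is in the denominator and how subjects without an assessment are counted. If the rate were computed only among those assessed, and some of those not assessed had failed treatment, the reported rate would be too high. The trial is open label, so these choices should be fixed before responses are tabulated.

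**Working it through.** The plan gives no precision, power or reference rate for CR, so it has no figure of that kind to reproduce.

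**Inputs**
- n = 15 (Trial Summary; Section 10.1 states 15 as a minimum).
- Number of responders: not given. I use 8 for illustration and scan the range of possible results.
- Number unassessed: not given. I assume 1 to 4 of 15.

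**Step 1: precision of one proportion.** The exact (Clopper-Pearson) 95% limits for x responders among n are

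lower = Beta quantile at 0.025 with parameters (x, n − x + 1)

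upper = Beta quantile at 0.975 with parameters (x + 1, n − x)

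| x/15 | Rate | 95% CI | Width (points) |
|---|---|---|---|
| 3 | 20.0% | 4.3 to 48.1% | 43.8 |
| 5 | 33.3% | 11.8 to 61.6% | 49.8 |
| 7 | 46.7% | 21.3 to 73.4% | 52.1 |
| 8 | 53.3% | 26.6 to 78.7% | 52.1 |
| 10 | 66.7% | 38.4 to 88.2% | 49.8 |
| 12 | 80.0% | 51.9 to 95.7% | 43.8 |

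From 3/15 to 12/15 the width stays between 44 and 52 points. None of this needs a control group.

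**Step 2: effect of the denominator.** Hold responders at 8 and let u subjects be unassessed. Counting them as non-CR gives 8/15 = 53.3% for every u. Dropping them gives 8/(15 − u):

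| u (assumed) | Assessed-only rate | 95% CI | Difference from 53.3% (points) |
|---|---|---|---|
| 1 | 8/14 = 57.1% | 28.9 to 82.3% | 3.8 |
| 2 | 8/13 = 61.5% | 31.6 to 86.1% | 8.2 |
| 3 | 8/12 = 66.7% | 34.9 to 90.1% | 13.3 |
| 4 | 8/11 = 72.7% | 39.0 to 94.0% | 19.4 |

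**Step 3: would treatment failures be missing?** The provisions point both ways.
- Towards missing: Section 8.1.6.6 routes only completers and those stopping for reasons other than progression to the Week 19 cystoscopy. Section 8.1.6.5 says "Assessments at the Discontinuation/Safety Follow-Up Visit include a full physical examination, ECOG Performance Status and vital signs", and neither it nor the Section 7.1 flow chart places a cystoscopy at that visit.
- Against: the flow chart schedules recurrence status at the discontinuation visit, and its footnote b applies that visit to everyone who stops early, whatever the cause. Section 8.1.5.1 asks for the applicable final-visit activities at discontinuation. Recurrence status may also be collected by chart review (footnote g).

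A subject with documented progression would naturally be entered as CR = no. The loss of failures is therefore possible, but not built into the plan.

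**The case against.** The strongest reply is that descriptive reporting suits a small single-arm study. The formal objective in Section 3.2 is a rate, which is estimation; Section 5.8 concedes that 15 subjects cannot support a powerful analysis; and any reader can compute an interval from x/15. Most of this stands, and it limits the weight of the point. It does not justify the reason Section 10.1 gives for omitting an interval, nor supply a denominator or a missing-data rule, which a purely descriptive table also needs.

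A second reply is that counting everyone without an assessment at the nominal month as a non-responder would itself mislead. Section 8.1.4 and footnote d of the flow chart expect follow-up visits to drift, so a subject in remission seen off schedule could become a failure. This stands in full; any such rule needs a visit window.

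Four stronger inferences are tempting but not supported:
- That an interval would show whether MK-3475 changed the response pattern. A one-sample interval cannot do that, so the aim itself needs rewording.
- That subjects who progress are systematically lost and the CR rate is biased upwards. Recurrence status at discontinuation argues against this, and the documents give no count of unassessed subjects.
- That replaced subjects would dilute the rate. The replacement clause in Section 5.7 concerns a screened subject who withdraws before the first cycle, and no number of enrolled, untreated subjects is given.
- That Section 10.1 contradicts itself because it says of the questionnaires that "the responses may be analyzed to look for longitudinal effects over time for specific variables of interest with repeated measures ANOVA". That analysis is optional, is flagged as low in power, and looks at change within subjects from a pre-treatment value.

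**Conclusion.** The point holds, at the level of something that should be changed. The lack of a control group does not justify withholding an exact interval, and the stated 19-week aim goes beyond what the planned output can show. The interval widths of 44 to 52 points follow from n = 15 and results between 3/15 and 12/15, with no further assumption.

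The missing denominator and the missing rule for unassessed subjects are real gaps in the text, but their numerical effect is conditional. The range of 57% to 73% against 53% rests on an assumed 8 responders, an assumed 1 to 4 unassessed subjects, and a choice to drop them that the plan neither makes nor excludes.

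The consequence is limited: CR is secondary, and no dose or sample-size decision uses a CR interval.

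**What to change.** In Section 10.1, replace the sentence that rules out statistical analysis with text to this effect:

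*CR at each time point will be reported as n/N with an exact (Clopper-Pearson) 95% CI in all subjects who received or attempted at least one MK-3475 cycle; no formal comparison will be made.*

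Then add these counting rules:
1. Subjects with documented recurrence or progression at or before a time point count as non-CR at that time point.
2. Off-schedule assessments are assigned to time points by a visit window stated in advance.
3. Subjects with no assessment in the window count as non-CR in the main estimate, and their number is reported.
4. The rate among assessed subjects is shown alongside as a sensitivity result.

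Also in Section 10.1, replace the aim quoted above with one of estimating the CR rate.

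The cost is a few sentences and minor programming for each time point, with no added patients or assessments. The downside is that wide intervals become visible and the headline rate may be somewhat lower than an assessed-only figure.
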